5.3 Sample size

Based on data from previous studies of surgical patients receiving an active (arginine nutritional supplement) versus a control treatment, it is reasonable to assume that intervention-related effect sizes (changes in signaling activity) are about twice as large as pooled standard deviations. This has been noted for signaling molecules downstream of TLR4 in response to arginine supplementation. TLR4-signaling (NFkB) is the primary outcome of this proof-of-concept study. A sample size of 16 patients per group should therefore provide ~80% at p<0.05 to detect an intervention-related group differences.

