5.0 Statistical Measures

5.1 Outcome Measurements

The primary outcome is the cumulative NFkB signal in innate immune cells 1 and 24 hours after surgery.

Secondary outcomes include HMGB1 plasma levels, functional recovery trajectories (measured objectively with ActiGraph and subjectively with WOMAC function sub-scale), postoperative pain resolution (measured with WOMAC-pain subscale), and postoperative resolution of fatigue and resulting impairment of daily activities (measured with SRS). Trajectories will be reflected by the time to resolve function to mild impairment, the time to resolve pain to mild levels, and the time to resolve fatigue to 50% of maximum postoperative fatigue.

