5.2 Analysis Plan

Page 6 Protocol Version # 1 The primary outcome NFkB signaling in innate immune cells between the two study groups will be analyzed with a non-paired t-test. A similar exploratory analysis will be conducted for secondary outcomes. However, the study is powered to detect differences of the primary outcome.

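### Section 5.3 does not add up: a 2-SD effect with 16 per group gives power above 99.9%, not about 80%; 16 per group at 80% power matches about 1 SD

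*Combined protocol and SAP*

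**What the plan says.** The sample-size argument is in section 5.3. Its premise, taken from earlier data on an arginine supplement, is that "intervention-related effect sizes (changes in signaling activity) are about twice as large as pooled standard deviations". The support offered is: "This has been noted for signaling molecules downstream of TLR4 in response to arginine supplementation". The conclusion is: "A sample size of 16 patients per group should therefore provide ~80% at p<0.05 to detect an intervention-related group differences". The word *power* is missing from that sentence, but no other reading of the 80% makes sense.

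Section 5.2 names the test. The primary outcome "between the two study groups will be analyzed with a non-paired t-test", and the section adds that "the study is powered to detect differences of the primary outcome". Section 5.1 defines the endpoint: "The primary outcome is the cumulative NFkB signal in innate immune cells 1 and 24 hours after surgery".

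Allocation is equal (section 4.0) and planned enrolment is 36 (section 3.3). The plan gives no sidedness, no dropout rate, no multiplicity adjustment, and no mean or SD for the primary endpoint.

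**The concern.** The word *therefore* in section 5.3 makes the 2-SD effect the premise and the 80% the conclusion. A difference of 2 SD is very large for a two-sample comparison, and far fewer than 16 per group would normally detect it with 80% power. By contrast, 16 per group is the familiar answer for an effect of 1 SD.

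Section 5.2 rests its claim of adequate power on this paragraph alone. If the figures disagree, the reader is misinformed about the effect at which the design has about 80% power. That matters most when a null result is interpreted. As printed, the plan suggests that effects below 2 SD are poorly covered, when in fact the design covers effects well below that. It also leaves 16 per group without a stated justification.

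**Working it through.** **Inputs**

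- Standardised difference d: about 2 (section 5.3).
- n = 16 per group (section 5.3); equal allocation (section 4.0).
- Alpha 0.05 (section 5.3); sidedness not stated, so both are shown.
- Test: unpaired t-test (section 5.2).
- Assumption: d = 2 applies to the primary outcome, because section 5.3 uses it that way.

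**Formula.** The t statistic is noncentral t with df = 2n − 2 and noncentrality d × √(n/2). Power is the probability that it exceeds the critical value (in absolute value if two-sided).

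**Step 1: try to reproduce the plan's 80%.** df = 2 × 16 − 2 = 30 and noncentrality = 2 × √(16/2) = 5.657. Power is 0.9998 two-sided and 0.9999 one-sided. The stated figure is not reproduced; it is about 20 percentage points too low. A simulation of 400,000 two-sided trials also gave 0.9998.

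**Step 2: sample size that gives about 80% at d = 2.**

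| n per group | Power, two-sided | Power, one-sided |
|---|---|---|
| 4 | 0.657 | 0.802 |
| 5 | 0.791 | 0.892 |
| 6 | 0.876 | 0.942 |
| 16 | 0.9998 | 0.9999 |

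**Step 3: effect that gives 80% at n = 16.** Solving for d gives 1.024 two-sided and 0.900 one-sided. At exactly d = 1, two-sided power is 0.781 by the t distribution and 0.807 by the normal approximation. The usual normal formula at d = 1, two-sided, gives n = 2 × (1.960 + 0.842)² / 1² = 15.7, which rounds up to 16. So a 1-SD effect yields the plan's sample size exactly. That suggests where 16 came from, but the documents do not say so.

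**Step 4: can a looser reading close the gap at n = 16?**

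- *About twice* read as 1.5 SD: power is 0.984 two-sided and 0.994 one-sided.
- 16 in total, so 8 per group, at d = 2: 0.960 two-sided.
- Planned enrolment of 36, so 18 per group, at d = 2: 0.9999 two-sided.
- Patient loss (two-sided, d = 2): each group would have to fall from 16 to 6 or 5, a loss of 10/16 = 62.5% to 11/16 = 68.8%.
- Multiplicity (two-sided, d = 2): alpha would have to be about 0.00005. No adjustment is written.
- Larger endpoint SD: it would have to be 2/1.024 = 1.95 times the assumed one two-sided, or 2/0.900 = 2.22 times one-sided.

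The first three do not come near 80%. The last three would need a condition that the plan does not state.

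**The case against.** The strongest reply is that the 2-SD ratio may not be on the scale of the primary outcome. Section 5.3 attaches it to changes in signaling under arginine, whereas section 5.1 defines a cumulative signal at 1 and 24 hours with no baseline subtraction. The effect on the actual endpoint could then be nearer 1 SD. Two illustrations follow, two-sided with 16 per group. The correlations are assumed, since the documents give none.

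- *The ratio refers to change scores, but the test uses the post-surgery signal.* With equal variances and pre/post correlation r, d = 2 × √(2(1 − r)). For r = 0.5, d stays at 2. For r = 0.80, d = 1.26 and power is 93%. For r = 0.87, d = 1.02 and power is 80%.
- *The 2-SD effect occurs at only one of the two summed time points.* Then d = 2/√(2(1 + r)), with r the correlation between them. Power is 97% at r = 0, 88% at r = 0.5 and 80% at r = 0.9.

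So a route to 80% exists, but it needs high correlations and a step that section 5.3 does not contain. What stands is that the authors may have sized for a smaller effect on purpose, and that an undocumented step is as possible as a slip in calculation. This does not rescue the paragraph, which derives its power directly from the 2-SD figure.

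It is also fair to say that the practical impact is small. This is a proof-of-concept study, its secondary analyses are exploratory, and no interim look or success threshold depends on the 80%.

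**Conclusion.** The concern holds. The effect, sample size, alpha and power printed in section 5.3 cannot all be true under the test in section 5.2. The stated inputs give power above 99.9%, and the stated power belongs to an effect of 1.02 SD two-sided or 0.90 SD one-sided, about half the one assumed.

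This rests on applying the 2-SD ratio to the primary outcome, as the paragraph itself does. The SD of the cumulative endpoint is not in the documents, so the true power of the trial cannot be established from them, nor can it be said which figure is the misstatement. If 2 SD is right, the error is on the safe side. If the true effect is near 1 SD, power is about 80%, but the arginine data cited for 2 SD do not supply the basis for that. The paragraph should be fixed, but the error does not threaten the conduct or analysis of the trial.

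**What to change.** The authors should state whether the 2-SD effect or the 80% power was intended and whether the test is one- or two-sided, then rewrite section 5.3 so that the four figures agree. Possible wording, if two-sided:

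> With an unpaired t-test at two-sided alpha 0.05, 16 patients per group give 80% power to detect a difference of 1.02 pooled SD in the primary outcome; under a difference of 2 SD, power exceeds 99.9%.

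If the test is one-sided, 1.02 becomes 0.90. If an effect near 1 SD was the real target, the section should say so and give its basis, including how the arginine ratio carries over to the cumulative 1-hour and 24-hour endpoint.

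The cost is one paragraph of wording. Enrolment, allocation, the test and the primary outcome stay as they are.
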